4.2 Rationale for study design, doses and control groups

In a Phase IIb study conducted with D-CytoFab employing a loading dose of 250 units/kg followed by 9 doses of 50 units/kg every 12 hours, there was a significant, prompt and sustained suppression of plasma TNF α during treatment such that TNF α was undetectable in nearly all plasma samples obtained during the entire 5 days of active treatment. Modest and transient rises of TNF α in the treated group occurred in only 2 patients. These 2 patients had the highest baseline TNF α levels of the group, suggesting that dosing was in the optimal region. This dosing regimen was found to significantly improve clinical outcomes for the D-CytoFab-treated group with no adverse safety findings.

In a recently completed Phase IIa study (D0620C00004) conducted with AZD9773, similar effects on plasma TNF α were seen. This particular study was not powered to detect efficacy, but did demonstrate that loading doses of up to 750 units/kg and maintenance doses of up to 250 units/kg every 12 hours were well tolerated in patients with severe sepsis.

In this Phase IIb study, which is powered to detect an effect on the parameter of VFD as a measure of efficacy, both the 250/50 units/kg regimen and the 500/100 units/kg regimen will be evaluated to determine which dose regimen should be employed in further clinical studies to evaluate an effect of AZD9773 on 28-day mortality. Both of these dose regimens were well tolerated in the Phase IIa (D0620C00004) study and the 250 units/kg dose was also well tolerated in the earlier D-CytoFab study. A dose regimen lower than 250/50 units/kg was not included in this Phase IIb study because 250/50 units/kg produced significant clinical benefit with D-CytoFab and there is currently no tolerability concern with the doses chosen for this study. The higher dose will explore the possibility of increased benefit with more TNF α suppression and help define the therapeutic dose-response.

The optimal duration of therapy with an anti-TNF α agent is a balance between intervening to suppress TNF α bursts while not inhibiting the host inflammatory response for too long. A treatment period of 5 days was chosen for the Phase IIb study of D-CytoFab and for the recently completed Phase IIa study (D0620C00004) conducted with AZD9773. In this Phase IIb study the maximum treatment period will also be 5 days.

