7.3.2 Definitions of serious adverse event

A serious adverse event is an AE occurring during any study phase (ie, run-in, treatment, washout, follow-up), and at any dose of the IP or placebo, that fulfils one or more of the following criteria:

- Results in death. All deaths that occur between provision of informed consent and Day 90 must be reported on the statement of death page.
 - Deaths between provision of informed consent and Day 29, if considered unequivocally due to sepsis by the investigator, should **NOT** be reported as a SAE but should be recorded on the statement of death page.
 - Deaths between provision of informed consent and Day 29 if **NOT** considered unequivocally due to sepsis by the investigator should be reported as an SAE as well as on the statement of death page.
 - Deaths between Days 30 and 90 will **ONLY** be reported as a SAE if considered to be related to late-onset toxicity to the study drug by the investigator.
- Is immediately life-threatening.
- Requires in-patient hospitalisation or prolongation of existing hospitalisation.
- Results in persistent or significant disability or incapacity.
- Is a congenital abnormality or birth defect.
- Is an important medical event that may jeopardise the patient or may require medical intervention to prevent one of the outcomes listed above.

For reporting purposes, any suspected transmission via a medicinal product of an infectious agent is also considered an SAE and is reported in an expedited manner. Any organism, virus or infectious particle (for example prion protein transmitting transmissible spongiform encephalopathy), pathogenic or non-pathogenic, is considered an infectious agent.

For further guidance on the definition of a SAE, see [Appendix B](#) to the Clinical Study Protocol.

Note that SAEs that could be associated with any study procedure should also be reported. For such events the causal relationship is implied as “yes”.

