Deterioration as compared to baseline in protocol-mandated laboratory values, vital signs and other safety variables should only be reported as AEs if they fulfil any of the SAE criteria or are the reason for discontinuation of treatment with the IP. However, the investigator may record such findings as an AE at his/her discretion in addition to completing an unscheduled laboratory/vital signs page with the information on the clinically significant test abnormality. If a deterioration in a laboratory value/vital sign is associated with clinical signs and symptoms, the sign/symptom will be reported as an AE and the associated laboratory result/vital sign will be considered as additional information. Any new or aggravated clinically relevant abnormal medical finding at a physical examination, dermal examination or lung auscultation as compared with the baseline assessment will be reported as an AE. Clinically relevant deterioration in

██████████
unscheduled assessments of laboratory/vital signs/ECG parameters should be reported on additional eCRF pages.

Wherever possible, the reporting investigator uses the clinical, rather than the laboratory term (eg, anaemia versus low haemoglobin value).

Overdose

Please refer to Section 1.2.

Pregnancy

Please refer to Section 1.3.

Deaths

All deaths occurring from provision of informed consent until Day 90 must be reported on the statement of death page. The cause of death may be reported as a SAE based on the criteria described in Section 7.3.2.

Follow-up of unresolved adverse events

After the initial AE/SAE report the investigator is required to follow up proactively each patient and provide further information to PAREXEL Clinical Studies Safety Centre on the patient's condition. During the study all AE/SAEs should be followed up to resolution or until the patient completes the study (ie, Day 90 or death) unless the event is considered by the investigator to be unlikely to resolve due to the patient's underlying disease (in these cases, the investigators must record their opinions in the patient's medical records), or the patient is lost to follow-up. Events still present at the time of death, and that were not the cause of death, should be classified as "ongoing". AstraZeneca and/or PAREXEL retain the right to ask for further information on any AE, which may be considered of interest.

Other significant adverse events

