7.6.7 Infection assessment

The presence of infections will be monitored at the timepoints specified in [Table 1](#). At screening, the site of infection should be noted. All patients must have a blood culture prior to randomisation. The blood culture result does NOT have to be known prior to randomisation. The estimated date and time of presentation of all infections will be recorded. The time of all blood cultures will be recorded. Additional information will be collected for positive blood cultures. Positive culture results defining the index infection will also be recorded. Any subsequent positive culture will also be recorded. The site of infection, associated pathogen(s) and antimicrobial susceptibility for the associated pathogens will be recorded. In addition, infections will be classified as community acquired or healthcare associated. Healthcare associated will be defined as a patient meeting one or more of the following ([Niederman et al 2005](#)):

1. Hospitalisation for \geq 2 days in the preceding 90 days.

2. Residence in a nursing home or extended care facility.
3. Undergoing home infusion therapy (including antibiotics).
4. Chronic dialysis within the preceding 30 days.
5. Home wound care.
6. A family member with a multidrug-resistant pathogen.

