- A summary of the number and percentage of patients with a SAE outcome of death by treatment group and preferred term.
- A summary of the number and percentage of patients reporting any treatment-emergent OAE by treatment group, SOC and preferred term.
- A summary of the number and percentage of patients reporting any infection by treatment group, SOC, preferred term and category (healthcare-associated, community-acquired).

The following by-patient listings will be presented, each of which will follow the format described for AEs in Section [13.3.9.2](#).

- A by-patient listing of all SAEs.
- A by-patient listing of all OAEs.
- A by-patient listing of all deaths that occurred during the study.
- A by-patient listing of all AEs leading to withdrawal from study treatment.

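### Section 7.3.2 exempts sepsis deaths from SAE reporting without limiting this to the qualifying episode, so fatal new infections can be reported inconsistently and miss the fatal-SAE table

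*Protocol*

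**What the plan says.** Section 7.3.2 lists the SAE criteria and attaches special rules to the criterion of death. For "Deaths between provision of informed consent and Day 29, if considered unequivocally due to sepsis by the investigator", the instruction is that they should not "be reported as a SAE but should be recorded on the statement of death page". Other deaths in that window are SAEs. Deaths from Day 30 to Day 90 will only "be reported as a SAE if considered to be related to late-onset toxicity to the study drug by the investigator". The remaining SAE criteria are listed alongside without qualification, for example: "Requires in-patient hospitalisation or prolongation of existing hospitalisation".

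The paragraph on deaths in Section 7.3.3 refers back: "The cause of death may be reported as a SAE based on the criteria described in Section 7.3.2". Section 7.3.4, which sets the 24-hour site report and the one-calendar-day transfer of fatal events, does the same.

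The planned outputs in Section 13.3.9.3 include: "A summary of the number and percentage of patients with a SAE outcome of death by treatment group and preferred term". They also include a summary of infections by arm, a serious-event table by arm and a by-patient listing of all deaths. Section 13.3.9.2 counts deaths by arm in the overview table, and Section 13.3.7 compares mortality at 7, 28 and 90 days.

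**The concern.** In a sepsis trial it is reasonable not to expedite every death from the disease under study. The difficulty is that the exemption is defined by the word sepsis, not by the episode that brought the patient into the trial. A patient may recover from the qualifying infection, acquire a new one after the first infusion, become septic again and die. That death fits the exemption as written.

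This matters more for a TNF-neutralising drug than for most. Section 4.2 explains the 5-day course as "a balance between intervening to suppress TNF α bursts while not inhibiting the host inflammatory response for too long", so the plan itself recognises that suppressing host inflammation has a price. New infection is a natural place for that price to appear, and a fatal one would often look like sepsis. At stake is whether such deaths are reported in the same way at some 100 centres, and whether the study report can show them by arm.

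**Working it through.** No figure in the plan is in dispute, so this is a comparison of provisions with a note on scale.

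**1. Is the exemption limited to the index episode?** Sections 7.3.2, 7.3.3 and 7.3.4 contain no such limit. Elsewhere the protocol does make the distinction. Inclusion criterion 1 (Section 5.1) requires a first episode of sepsis in the hospitalisation, and Section 7.6.7 states: "Positive culture results defining the index infection will also be recorded. Any subsequent positive culture will also be recorded". The distinction is available in the data but is not carried into the SAE rule.

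**2. Which rule prevails?** A new infection that threatens life or prolongs the hospital stay meets SAE criteria in Section 7.3.2. If it then kills through sepsis, the same section says the death is not to be reported as an SAE. It gives no order of precedence.

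**3. The same case under two readings.** The patient has a new infection after the first infusion and dies of sepsis before Day 29.

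- *Reading A:* the infection is reported as an SAE when it becomes life-threatening or prolongs the stay. Section 7.3.3 records an outcome for each event, so the outcome can become death. The case follows the Section 7.3.4 timelines and enters the fatal-SAE table.
- *Reading B:* the site treats the course as a sepsis death and completes only the statement of death page. The infection may be entered as a non-serious event. No SAE death is reported, and the case is not in the fatal-SAE table.

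Both readings are consistent with the text.

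**4. Where the Reading B case still appears.** It is in the overview death count, the mortality endpoints, the deaths listing and the mortality rates reviewed by the IDMC, and in the any-infection summary if the infection was recorded. None of these is specified as cause of death by arm. The any-infection summary is split into healthcare-associated and community-acquired, not by fatal outcome or by index versus new infection.

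**5. Scale.** The earlier D-CytoFab study had 28-day mortality of 26% and 37% in its two arms (Section 2.4). Applied to this trial:

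- 300 × 0.26 = 78 deaths
- 300 × 0.37 = 111 deaths

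That is 26 to 37 per 100-patient arm. It is the number of deaths needing the attribution judgement, not the number misreported.

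**6. Illustration on assumed rates that are not in the documents.** Suppose fatal new infections occur in 6% of 200 active patients (12) and 2% of 100 placebo patients (2), and a share s is handled under the exemption. The fatal-SAE table then shows 12(1 − s) against 2(1 − s):

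- s = 0: 12 against 2, an excess of 4 per 100
- s = 0.5: 6 against 1, an excess of 2 per 100
- s = 1: 0 against 0, no excess

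The visible excess falls in proportion to s. Neither the rates nor s can be taken from the protocol.

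**The case against.** The strongest reply is that the exemption concerns deaths, not infections. A new infection after dosing is a treatment-emergent AE (Section 7.3.1). It is an SAE if it is life-threatening or prolongs hospitalisation, and it then follows the 24-hour route and can carry a fatal outcome. Secondary infections are assessed at Days 29 and 90, the IDMC sees unblinded data, and the word unequivocally narrows the exemption. A table by cause could also be specified in an analysis plan that is not shown here.

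Much of this stands, and it rules out several stronger readings that a reader might infer:

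- *That these deaths necessarily bypass SAE reporting.* Reading A shows they need not.
- *That the safety conclusion would be wrong as reported.* Every death enters the by-arm mortality comparisons, so an excess of deaths would count there. The limitation is that the trial is not powered for mortality, and fewer index-sepsis deaths could offset more new-infection deaths.
- *That 39 to 100 deaths are hidden.* That range comes from assuming 50% to 90% of the 78 to 111 deaths are called sepsis (0.5 × 78 = 39; 0.9 × 111 ≈ 100). The share has no source in the protocol. The range covers all sepsis-attributed deaths, including index-episode deaths, which a corrected rule would still exempt.
- *That the protocol names fatal secondary infection as the main expected harm.* Section 4.2 discusses treatment duration and does not say this.

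What the reply does not answer is the silence on precedence. Nor can a later analysis plan restore a site report that was never made.

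**Conclusion.** The point holds as a defect in a reporting rule. Section 7.3.2 neither ties the exemption to the qualifying episode nor says how it ranks against the other SAE criteria. Identical fatal new infections can therefore be reported as SAEs at one site and only on the death page at another, and the fatal-SAE table inherits that inconsistency. The loss is limited to consistent reporting and by-arm attribution of fatal new infections; the deaths themselves are still counted. The number affected cannot be estimated from the documents. It depends on how often fatal new infections occur and how sites read the rule, and the protocol gives neither. The conclusion rests on the protocol text alone, and it is a worthwhile, inexpensive clarification rather than a threat to the primary analysis.

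**What to change.** In Section 7.3.2, limit the exemption to deaths unequivocally due to the index septic episode. State that a fatal new or secondary infection starting after the first infusion is reported as an SAE, which also settles precedence for those cases.

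In Section 13.3.9.3, add a table of all deaths in the safety population by arm and cause (index sepsis, new infection, other), to Day 29 and to Day 90, taken from the statement of death page. Supply the same table to the IDMC.

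The page is already required for every death to Day 90, so the cost is a short amendment to Section 7.3.2, one further table and a modest number of extra SAE reports. Patient treatment is unchanged.

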Causality of adverse events

The investigator will assess causal relationship between IP and AEs, and answer “yes” or “no” to the question “Do you consider that there is a reasonable possibility that the event may have been caused by the IP.

AEs will be recorded in the eCRF as being related or not-related to study drug. For an AE to be a suspected drug-related event, there should be at least a reasonable possibility of a causal relationship between the study medicinal product and the AE. If an AE is considered to be related to treatment(s) other than the study drug, this treatment must be named in the eCRF.

For SAEs, causal relationship will also be assessed for study procedures.

For SAEs that could be associated with any study procedure, the causal relationship is implied as “yes”.

A guide to the interpretation of the causality question is found in [Appendix B](#).

Adverse events based on signs and symptoms

All AEs spontaneously reported by the patient or reported in response to the open question from the study personnel: “Have you had any health problems since the previous visit?”, or revealed by observation will be collected and recorded in the eCRF. When collecting AEs, the recording of diagnoses is preferred (when possible) to recording a list of signs and symptoms. However, if a diagnosis is known and there are other signs or symptoms that are not generally part of the diagnosis, the diagnosis and each sign or symptom will be recorded separately.

Adverse events based on examinations and tests

The reporting of laboratory/vital signs/ECG abnormalities as both abnormalities and AEs should be avoided.

Deterioration as compared to baseline in protocol-mandated laboratory values, vital signs and other safety variables should only be reported as AEs if they fulfil any of the SAE criteria or are the reason for discontinuation of treatment with the IP. However, the investigator may record such findings as an AE at his/her discretion in addition to completing an unscheduled laboratory/vital signs page with the information on the clinically significant test abnormality. If a deterioration in a laboratory value/vital sign is associated with clinical signs and symptoms, the sign/symptom will be reported as an AE and the associated laboratory result/vital sign will be considered as additional information. Any new or aggravated clinically relevant abnormal medical finding at a physical examination, dermal examination or lung auscultation as compared with the baseline assessment will be reported as an AE. Clinically relevant deterioration in

██████████
unscheduled assessments of laboratory/vital signs/ECG parameters should be reported on additional eCRF pages.

Wherever possible, the reporting investigator uses the clinical, rather than the laboratory term (eg, anaemia versus low haemoglobin value).

Overdose

Please refer to Section 1.2.

Pregnancy

Please refer to Section 1.3.

Deaths

All deaths occurring from provision of informed consent until Day 90 must be reported on the statement of death page. The cause of death may be reported as a SAE based on the criteria described in Section 7.3.2.

Follow-up of unresolved adverse events

After the initial AE/SAE report the investigator is required to follow up proactively each patient and provide further information to PAREXEL Clinical Studies Safety Centre on the patient's condition. During the study all AE/SAEs should be followed up to resolution or until the patient completes the study (ie, Day 90 or death) unless the event is considered by the investigator to be unlikely to resolve due to the patient's underlying disease (in these cases, the investigators must record their opinions in the patient's medical records), or the patient is lost to follow-up. Events still present at the time of death, and that were not the cause of death, should be classified as "ongoing". AstraZeneca and/or PAREXEL retain the right to ask for further information on any AE, which may be considered of interest.

Other significant adverse events

During the evaluation of the AE data, medically qualified experts on the study team will review the safety data to select significant AEs of particular clinical importance/special interest, which will be considered other significant AEs (OAEs) / events of special interest and reported as such in the Clinical Study Report.

Infusion reactions

Full details on classifying infusion reactions are provided in [Appendix D](#). In the event a patient experiences a hypersensitivity reaction, a blood sample for tryptase, IgE and quantitative eosinophil count should be obtained at 20 to 60 minutes post suspected infusion or hypersensitivity reaction and at Day 29 (see [Table 1](#)).

Worsening adverse events present at baseline

Conditions present at baseline will be recorded. If such a condition worsens or deteriorates, it will be recorded as an AE/SAE with the onset date corresponding to the date that it worsened from its baseline intensity.

7.3.4 Reporting of serious adverse events

All SAEs have to be reported, whether or not considered causally related to the investigational product, or to the study procedure(s). All SAEs will be recorded in the eCRF. Death may be reported as a SAE based on the criteria described in Section 7.3.2.

If any SAE occurs in the course of the study, then investigators or other site personnel inform appropriate PAREXEL representatives within 24 hours of becoming aware of the SAE.

The designated PAREXEL representative works with the investigator to ensure that all the necessary information is provided to the AstraZeneca Patient Safety data entry site **within one calendar day*** of initial receipt for fatal and life-threatening events and **within five calendar days** of initial receipt for all other SAEs.

For fatal or life-threatening AEs where important or relevant information is missing, active follow-up is undertaken immediately. Investigators or other site personnel inform PAREXEL representatives of any follow-up information on a previously reported SAE within 24 hours.

[figure not shown]
Follow up information should be sent to AstraZeneca Patient Safety within the same timelines as the initial report unless any follow-up information indicates a change in the SAE from serious to fatal or life-threatening: this information needs to be forwarded to AstraZeneca Patient Safety within one calendar day*.

Initial and follow-up SAE information will be reported using paper SAE reporting forms.

* For fatal and life-threatening events the PAREXEL representative sends the report on the day that they first become aware of it. If this is not possible, it can be sent as early as possible on the next business day. If the report is received after normal business hours, for instance during a weekend or public holiday, the information is forwarded as early as possible on the first business day following the weekend or holiday.

Investigators or other site personnel send the relevant SAE report by fax to the designated PAREXEL representative.

The investigator will submit a paper SAE report to:

	Fax number	Hotline number	Emergency contact number
North America			
Europe and South Africa			
Australia			
South America			

SAE information will also be entered and submitted into the WBDC system on the relevant eCRF modules. SAE and AE data entered into the eCRF does not need to meet the same timelines but should be done in a timely manner.

The reference document for definition of expectness/listedness of adverse drug reactions is the IB.

